19.3. Changes to Final Study Protocol

All protocol amendments must be submitted to the ethics committee and regulatory authorities if required by local law. Protocol modifications that affect subject safety, the scope of the investigation, or the scientific quality of the study must be approved by the ethics committee before implementation of such modifications to the conduct of the study. If required by local

CONFIDENTIAL

The information contained herein may not be used, disclosed, or published without the written consent of Biogen MA Inc.

law, such modifications must also be approved by the appropriate regulatory agency prior to implementation.

However, Biogen may, at any time, amend this protocol to eliminate an apparent immediate hazard to a subject. In this case, the appropriate regulatory authorities will be notified subsequent to the modification.

In the event of a protocol modification, the ICF may require similar modifications (see Section 17).

19.4. Ethics Committee Notification of Study Completion or Termination

Where required, the regulatory authorities and ethics committees must be notified of completion or termination of this study, and sent a copy of the study synopsis in accordance with necessary timelines.

19.5. Retention of Study Data

The minimum retention time for study records will meet the strictest standard applicable to that site, as dictated by any institutional requirements or local, national, or regional laws or regulations. Prior to proceeding with destruction of records, the Investigator must notify Biogen in writing and receive written authorization from Biogen to destroy study records. In addition, the Investigator must notify Biogen of any changes in the archival arrangements, including but not limited to archival at an offsite facility or transfer of ownership if the Investigator leaves the site.

19.6. Study Report Signatory

Biogen will designate one or more of the participating Investigators as a signatory for the study report. This determination will be made by several factors, including but not limited to the Investigator's experience and reputation in the studied indication; the Investigator's contribution to the study in terms of design, management, and/or subject enrollment; or by other factors determined to be relevant by Biogen.

CONFIDENTIAL

The information contained herein may not be used, disclosed, or published without the written consent of Biogen MA Inc.

1 INTRODUCTION

Study 221AD205 was a Phase 2, multicenter, randomized, parallel-group, double-blind, controlled study in participants with mild cognitive impairment (MCI) due to Alzheimer's disease (AD) or with mild AD dementia, with a randomized treatment period followed by an optional long-term extension period. The primary study objective was to assess the safety impact of continuing aducanumab (BIIB037) dosing in asymptomatic amyloid-related imaging abnormalities (ARIA) in participants with MCI due to AD or mild AD dementia.

Eligible participants were randomized (1:1) at Visit 1 to 1 of 2 groups that differed in terms of the management of asymptomatic ARIA found on magnetic resonance imaging (MRI) during the randomized treatment period. All randomized participants received aducanumab titrated up to 10 mg/kg (identical titration protocol as in the phase 3 program). In certain cases of asymptomatic ARIA as described in the study protocol, Group 1 participants were required to suspend or discontinue aducanumab dosing whereas the Group 2 participants were to continue aducanumab treatment. In these cases, to maintain the study blind, Group 1 participants were to receive placebo.

Termination of the study was announced on 21 March 2019, based on the results of an interim futility analysis in the aducanumab Phase 3 studies 221AD301 and 221AD302. Enrollment and dosing in 221AD205 were halted immediately upon the announcement. All participants were to return to the site within 4 weeks of the announcement to do the EOT (week 54) visit, and again 18 weeks after their last dose for the final follow up visit (Week 70). Due to the small amount of data collected in this study, only a synopsis clinical study report is planned.

The purpose of this statistical analysis plan (SAP) is to describe the analyses that are planned for the final report. The primary endpoint and most secondary endpoints of the study will not be evaluable due to the small actual sample size and short exposure time. Instead, the focus of the final analysis is summarizing the available baseline, exposure, and adverse event data that were collected during the study.

2 STATISTICAL ANALYSIS METHODS

2.1 General Considerations

Summary tables will be presented using descriptive summary statistics. For continuous variables, summary statistics will generally include: number of participants with data, mean, standard deviation, median, minimum and maximum. For categorical variables, this will generally include: number of participants in the analysis population, number with data, and the percent of those with data in each category. Due to the minimal amount of data collected in the study, most endpoints will not be summarized; instead, listings will be provided. Any straightforward listings that are routinely produced for Biogen clinical studies will not necessarily be mentioned in this plan.

Unless otherwise specified, summaries will be presented by study group and overall. Each table will typically have three columns, ordered as follows: Group 1, Group 2, and BIIB037 Total. Summaries presented by decreasing or increasing frequency will be sorted based on the aducanumab total column.

2.2 Analysis Study Group

Data will be analyzed by study group based on randomization. A listing of any participants who were dosed contrary to their randomization study group will be presented. This includes any Group 1 participant who received accidental aducanumab during an ARIA episode when placebo should have been administered, and any Group 2 participant who accidentally received placebo.

2.3 Analysis Populations

The follow analysis populations will be utilized in the interim analysis:

- Safety population:
The safety population is defined as all randomized participants who received at least one dose of aducanumab.
- Safety MRI population:
The safety MRI population is defined as all randomized participants who received at least one dose of aducanumab and had at least one post-baseline MRI assessment.
- Differential study treatment population:
The differential study treatment population is defined as all participants in the safety MRI population who experienced asymptomatic ARIA resulting in assignment of at least one infusion of study treatment that would have been different had the participant been in the other study group. Any Group 1 participant who receives placebo is in the differential study treatment population, as is any Group 2 participant who would have received placebo had they been assigned to Group 1. If there are few or no subjects in the differential study treatment population, analyses in this population may be omitted.

2.4 Background Characteristics

Background characteristics will be summarized based on the safety population.

2.4.1 Accounting of Participants

Disposition of participants will be summarized. This will include number of participants randomized and dosed, as well as the number and percentage of participants who completed each visit.

The reasons for treatment discontinuation and study withdrawal will be summarized. Because study termination was not a check box option on the End of Treatment and End of Study electronic case report forms (eCRFs), the reason will be categorized as “Study Termination” in the summary based on study team review of the verbatim reason provided on the eCRF, the date of last dose, and date of withdrawal. The reasons provided on the eCRFs will be listed.

The number of participants in each analysis population will be summarized.

2.4.2 Demographics and Baseline Characteristics

Demographic data including age, gender, ethnicity, and race will be summarized.

Summary of the baseline characteristics of AD includes laboratory ApoE ϵ 4 genotype, baseline clinical stage (MCI due to AD or mild AD), number of years of formal education, number of years since first AD symptoms, and number of years since diagnosis of AD.

Medical history and previous therapies for AD will be listed.

2.4.3 Concomitant Medications and Non-Drug Therapies

All concomitant medications will be coded using the World Health Organization (WHO) medication dictionary. All concomitant non-drug therapies will be coded using the MedDRA dictionary. All reported concomitant medications/therapies will be listed, regardless of start and stop dates.

2.4.4 Study Drug Exposure

The number of aducanumab infusions received will be summarized. A listing of all study drug administration records will be provided, including any placebo infusions.

2.5 Adverse Events

In general, the safety population will be used for analyses of adverse events. Where applicable for ARIA analyses, the safety MRI population may be used.

Adverse events will be included in the summaries based on the principle of treatment emergence. Treatment emergent is defined as having an onset date that is on or after the start of study treatment, or as worsening after the start of study treatment. For AEs with missing or partial start or stop dates, all available information will be used to determine if the event was treatment-emergent. If it cannot be ascertained based on partial information, the AE will be assumed to be treatment-emergent.

A listing of all AEs, whether treatment-emergent or not, will be provided.

2.5.1 Incidence of adverse events

The overall summary of AEs will present the number of participants with any AE, with any AE by maximum severity, with any related AE (related to study drug as assessed by investigator), with any SAE, with any related SAE, with an AE leading to study drug discontinuation, with an AE leading to study withdrawal, and the number of deaths.

Adverse events will be coded using the Medical Dictionary for Regulatory Affairs (MedDRA). The incidence of AEs by MedDRA system organ class and preferred term will be presented by decreasing frequency. Depending on the number of SAEs, this table may be repeated for serious events.

2.5.2 ARIA

2.5.2.1 ARIA Events

Since the diagnosis of ARIA requires brain MRI findings, ARIA data were collected under two data sources: (1) safety MRI data as recorded on brain MRI worksheet by central MRI reader; (2) AE electronic case report form. For each ARIA event, the information of start/end date, severity, location(s) in brain regions and evolution status on MRI scan is collected from the brain MRI worksheet by central MRI reader. ARIA severity on MRI is determined by central MRI reader based on number of brain regions involved and size of ARIA lesions on imaging. An AE record was then entered into the eCRF with the start/end date and severity information from brain MRI worksheet, and with information on the symptomatic status and action taken with study drug. If ARIA was symptomatic, the symptoms were entered into the AE eCRF. The AE eCRF data will be used as the primary source for ARIA analysis as it contains the complete information on ARIA as well as associated symptoms; unless otherwise specified, analyses of incidence or incidence rates are based on AE eCRF data.

ARIA types include ARIA-E (vasogenic edema) and ARIA-H (hemorrhage). ARIA-H includes ARIA-H microhemorrhage, ARIA-H macrohemorrhage and ARIA-H superficial siderosis.

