11.2.1.1. ARIA-E Cases

The management and disposition of subjects who develop ARIA-E during the randomized treatment period are detailed in [Table 5](#).

All subjects who develop ARIA-E should have unscheduled visits every 4 weeks (± 5 days) for follow-up MRI and ARIA safety assessments (as detailed in Section 5, [Table 1](#)), until the ARIA-E has resolved per centrally read MRI. [REDACTED] PK samples will be collected at the first unscheduled visit following an episode of ARIA.

Subjects who continue dosing during the first or subsequent recurring ARIA-E events will do so in accordance with the aducanumab dosing regimen (for details, see Section 11.2.3).

Subjects for whom treatment is temporarily suspended due to the first or recurrent ARIA-E events may resume treatment at the same dose, once ARIA-E and (if present) clinical signs and symptoms have resolved, in the treating HCP's opinion (for details see Section 11.2.3).

Management of ARIA-E after it resolves is described in Section 11.2.4.

Subjects who continue dosing during an ARIA-E event or who suspend dosing (including due to an ARIA-E event) should complete all scheduled clinic visits for assessments (as detailed in Section 5, [Table 1](#)). Subjects who permanently discontinue treatment due to ARIA-E (as with subjects who discontinue for other reasons) are to remain in the study and follow a modified schedule for tests and assessments until the end of study or withdrawal of consent ([Table 4](#)). This is in addition to completing the unscheduled visits as described above.

Subjects who withdraw from the study are to return for a safety follow-up visit 18 weeks after their last dose of study treatment.

CONFIDENTIAL

The information contained herein may not be used, disclosed, or published without the written consent of Biogen MA Inc.

Table 5: Disposition of ARIA-E Cases During Randomized Treatment Period

Clinical Symptom Severity (if present)	ARIA-E Severity on MRI (Central Read)				
	Mild	Moderate	Severe		
Asymptomatic	Stage 1				
Group 1	Continue dosing at current dose and schedule	Suspend dosing and receive placebo . Once ARIA-E resolves the subject may resume dosing at the same dose.	Suspend dosing (without receiving placebo). Once ARIA-E resolves, subject may resume dosing at same dose		
Group 2	Continue dosing at current dose and schedule ¹				
Asymptomatic	Stage 2				

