15.2. Safety Classifications

15.2.1. Investigator Assessment of Events

All events must be assessed to determine the following:

- If the event meets the criteria for an SAE as defined in Section 15.1.2
- The relationship of the event to study treatment as defined in Section 15.2.2
- The severity of the event as defined in Section 15.2.3

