15.2.3. Severity of Events

The following definitions should be considered when evaluating the severity of AEs and SAEs:

Severity of Event	
Mild	Symptoms barely noticeable to subject or does not make subject uncomfortable; does not influence performance or functioning; prescription drug not ordinarily needed for relief of symptoms but may be given because of personality of subject.
Moderate	Symptoms of a sufficient severity to make subject uncomfortable; performance of daily activity is influenced; subject is able to continue in study; treatment for symptoms may be needed.
Severe	Symptoms cause severe discomfort; symptoms cause incapacitation or significant impact on subject’s daily life; severity may cause cessation of treatment with study treatment; treatment for symptoms may be given and/or subject hospitalized.

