15.3.2. Adverse Events of Special Interest

An AE of special interest is an AE of scientific and medical concern specific to this study, for which ongoing monitoring and reporting are required. ARIA-E and ARIA-H are considered AEs of special interest and will be entered on the Adverse Event of Special Interest CRF within 72 hours following the receipt of abnormal MRI findings from the central MRI reader.

AE reporting for ARIA-E and ARIA-H will be based on the following centrally read MRI sequences: fluid attenuated inversion recovery/T2 for ARIA-E and T2*/gradient echo for ARIA-H.

If the event qualifies as an SAE, an SAE form should be submitted per the guidelines in Section 15.3.4. Investigators should include a copy of the centrally read MRI report when submitting the SAE form to Biogen.

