15.6. Safety Responsibilities

15.6.1. The Investigator

The Investigator's responsibilities include fulfilling all roles and responsibilities listed in Section [7.2](#). Additionally, the Investigator's responsibilities include the following:

- Monitor and record all AEs, including SAEs, on the CRF regardless of the severity or relationship to study treatment.
- Determine the seriousness, relationship, and severity of each event.
- Determine the onset and resolution dates of each event.
- Monitor and record all pregnancies and follow up on the outcome of all pregnancies in female subjects.
- Complete an SAE form for each SAE and fax it to Biogen within 24 hours of the site staff becoming aware of the event.
- Pursue SAE follow-up information actively and persistently. Follow-up information must be reported to Biogen within 24 hours of the site staff becoming aware of new information.
- Ensure all AE and SAE reports are supported by documentation in the subjects' medical records.
- Pursue AE follow-up information, if possible, until the event has resolved or become stable. Record AE follow-up information, including resolution, on the CRF, as applicable.
- Report SAEs to local ethics committees, as required by local law.

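### On the SAP's text, ARIA enters Table 6 at its MRI grade; unless the eCRF also holds a protocol 15.2.3 severity, the maximum-severity rows mix scan grade with symptom severity

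*SAP*

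**What the plan says.** **SAP.** Section 2.5.2.1 describes two data sources for ARIA, the central reader's MRI worksheet and the AE eCRF. It links them as follows: "An AE record was then entered into the eCRF with the start/end date and severity information from brain MRI worksheet". The worksheet grade reflects how many brain regions are involved and how large the lesions are. Symptomatic status, and any symptoms, also go into the AE eCRF. The eCRF is the working source: "unless otherwise specified, analyses of incidence or incidence rates are based on AE eCRF data".

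Section 2.5.1 defines the overall AE summary, which is SAP Table 6 (not protocol Table 6, which covers ARIA-H disposition). It reports "the number of participants with any AE, with any AE by maximum severity". Under SAP 2.1 the columns are Group 1, Group 2 and total. Nothing says how ARIA is to be graded in these rows.

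**Protocol.** Section 15.2.1 requires, for all events, an assessment of "The severity of the event as defined in Section 15.2.3". In 15.2.3 the mild category reads "Symptoms barely noticeable to subject or does not make subject uncomfortable; does not influence performance or functioning". Moderate and severe are defined by increasing discomfort and effect on daily life. Section 15.6.1 has the investigator "Determine the seriousness, relationship, and severity of each event". Section 15.3.2 states that "ARIA-E and ARIA-H are considered AEs of special interest" and sets no separate severity scale for them.

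**The concern.** Two scales share the labels mild, moderate and severe. One describes a scan and the other describes how unwell the participant was. Protocol Tables 5 and 6 keep them on separate axes, and protocol 16.2.2.2 planned to report ARIA severity from both the imaging and the clinical side. On the SAP's text they meet in one row.

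This matters more here than in most trials, because the question is whether dosing through symptom-free ARIA is safe. The primary endpoint would have isolated clinical impact, but SAP 2.5.2.2 says it will not be evaluated. SAP Table 6 is one of ten planned tables. Table 10 is specified by ARIA type only, so no planned table separates scan grade from symptom severity.

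**Working it through.** The plan gives no figure to reproduce. The check follows a record through the two texts, sizes the effect from a prior study, and then asks whether the groups are affected differently.

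**1. One participant, two gradings.** Take a participant whose only AE is an asymptomatic ARIA-E.

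| Grade on MRI | Severity under SAP 2.5.2.1 and 2.5.1 | Wording of protocol 15.2.3 that fits |
|---|---|---|
| Moderate | Moderate | Mild (no symptoms) |
| Severe | Severe | Mild (no symptoms) |

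**2. Illustrative size.** The inputs are in protocol 16.7. In Study 221AD103, of 185 participants, 20 had asymptomatic moderate ARIA-E and 1 had asymptomatic severe ARIA-E. Those grades are read here as MRI severity.

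- Share affected: (20 + 1)/185 = 21/185 = 11.4% (exact 95% CI 7.2% to 16.8%).
- Lower end of the shift in the moderate-or-severe share: 0 points, if each of the 21 had another AE at least as severe.
- Upper end: 11.4 points, if none did.

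These are not bounds for this trial. Study 221AD103 mixed dose levels, whereas all participants here were to titrate to 10 mg/kg. Its data include an extension, whereas SAP section 1 reports short exposure here. ARIA-H is left out because its grade split is not given. The documents give no sample size or event count for the terminated trial.

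**3. Do the groups differ?** Protocol Tables 5 and 6, for asymptomatic ARIA in the randomized period:

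| MRI grade | Stage 1 | Stage 2 |
|---|---|---|
| Mild | Both groups continue | Both groups continue |
| Moderate | Group 1 suspended on placebo; Group 2 continues | Same as Stage 1 |
| Severe | Same in both groups | Group 1 on placebo; Group 2 continues, except after a severe ARIA-E in Stage 1 (Table 5, footnote 1) |

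Symptomatic ARIA and macrohemorrhage are handled alike in both groups. The first infusion that differs by assignment can therefore come only after the MRI grade has reached at least moderate. SAP Table 6 uses the maximum, so on MRI grading that participant is already in the moderate-or-severe count in either group. Later dosing cannot add the participant to that count through scan grade. It can only move the participant from moderate to severe.

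**4. Size of the moderate-to-severe move.** This needs the chance of progression on the scan under continued dosing and under suspension. The documents give neither. The single severe case (1/185 = 0.5%) does not supply it, because protocol 4.4 describes Study 221AD103 as suspending or discontinuing dosing for moderate and severe asymptomatic ARIA.

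**The case against.** **The eCRF may already hold the right severity.** The protocol requires an investigator severity for every event, and 15.3.2 gives ARIA its own CRF. If sites complied, a 15.2.3 severity exists and the MRI grade may sit in a separate field. This stands as a possibility, since the eCRF is not in the documents. But MRI severity is the only severity the SAP mentions for the ARIA record, so a programmer working from the SAP would use it.

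**If the SAP fixes MRI grade as the ARIA severity, it has disclosed a rule.** This stands in part. SAP 2.5.2.1 describes how the record was filled. It does not label the rows of Table 6, and it does not reconcile them with protocol 15.2.3.

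**The report is a descriptive synopsis and everything is listed.** No hypothesis test is planned, both groups are handled alike, and all AEs, all ARIA events and the MRI assessments of participants with ARIA will be listed. This limits the consequence. Listings make a case traceable but do not correct or label the counts.

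**A stronger reading does not stand.** A reader might infer that grading by scan would make Group 2 show more moderate-or-severe AEs because it is dosed through ARIA, or that 11.4 points measures a distortion between groups. Step 3 of the working rules out the first for the combined count. The 11.4 points is a change of label expected in both arms.

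**Conclusion.** The point holds as a minor one. On the SAP's text, the maximum-severity rows of Table 6 would count symptom-free ARIA by scan grade alongside other AEs graded by symptoms, contrary to the scale the protocol sets for every event. This is conditional on there being no 15.2.3 severity for ARIA in the eCRF, or on that field not being used.

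The main effect is a relabelling common to both groups, illustrated at 0 to 11.4 points in the moderate-or-severe share. That range assumes the Study 221AD103 grades are MRI grades and that its ARIA-E rate carries over. A between-group effect through scan grade is possible only within the moderate-or-severe total, as a move from moderate to severe in Group 2, and its size cannot be derived from the documents.

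**What to change.** In SAP 2.5.1, state which severity ARIA contributes to Table 6.

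- If the eCRF holds a protocol 15.2.3 severity for ARIA, use it.
- If it holds only the MRI grade, show the maximum-severity rows twice. The first set covers all AEs, with a footnote that ARIA is graded by MRI. The second set leaves out the ARIA terms but keeps ARIA symptoms that were entered as AEs of their own.

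The cost is at most 3 extra rows × 3 columns = 9 cells, plus one footnote, and no new data. The downside is that symptoms recorded only inside the ARIA record, without a severity of their own, drop out of the second set. The footnote must say so.
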